SAP Modifiable prognostic factors of high cost related to healthcare utilization among older people seeking primary care with a new episode of back pain - an identification and replication study (working title)

stations established within each recruiting area. Follow-up questionnaires will be sent at 3, 6, and 12 months after inclusion for completion at home. All questionnaires are preferably completed electronically using the Infopad system, but paper versions will be available for patients not familiar with electronic data collection. All information will be stored and analysed securely through Service for sensitive data (TSD) at the University of Oslo, Norway.

BACE-D: At baseline all patients responded to a comprehensive questionnaire and went through a standardized physical examination. Follow-up questionnaires were sent (by e-mail or postal) at 3, 6, 9 and 12 months after inclusion.

Variables

Outcome variable

The outcome of this study is costs related to healthcare utilization aggregated for one year of follow up and dichotomized as high and low. Having high costs related to healthcare utilization is defined as patients with costs in the top 25th percentile [2, 3].

Healthcare utilization within the BACE-N and the BACE-D will be self-reported and include; consultation to healthcare professionals (type and frequency), number of diagnostic examinations (type and frequency), number of days of hospitalization and/or institutionalisation (only included in the BACE-N), back operations and use of back medication (both prescription and over-the-counter, type and frequency). All variables, except back operations, will be reported with a 3 month recall period at 3, 6, and 12 months follow-up for the BACE-N, at 3, 6, 9, and 12 months follow-up for the BACE-D. Back operations will be reported with a 12 month recall period at 12 months follow-up.

Healthcare utilization during the one year of follow-up will be described as shown in table 3 (BACE-N and BACE-D). The total cost of healthcare utilization will be estimated based on information presented in table 3 and unit costs of healthcare resources collected from national pricelists in Norway and the Nederlands (see table 1).

Potential modifiable prognostic factors

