First, type and frequency of use of different healthcare resources will be calculated for each of the follow-up periods; from baseline to 3 months, 3 to 6 months, and 9 to 12 months for the BACE-N study, and from baseline to 3 months, 3 to 6 months, 6 to 9 months, and 9 to 12 months for the BACE-D. Healthcare utilization will be presented as shown in table 3.

Next, costs will be estimated based on information presented in table 3, and unit costs of healthcare resources collected from national pricelists in Norway and the Nederlands (see table 1). Costs related to back medication will be estimated based on medication type (not exact medication name) and frequency of use. Data on dosage is not available. All costs will be presented in Euros (€) 2020. Costs of healthcare utilization will be described with median and interquartile range for the entire follow-up period as shown in table 4.

Identification analysis

Univariable and multivariable binary logistic regression models will be used to investigate individual association (crude and adjusted for selected covariates) between each predefined prognostic factor and costs related to healthcare utilization (within the BACE-N). The cost score will be entered into the model as a dependent dichotomous variable (high cost defined as patients with cost in the top 25th percentile, yes/no). The results will be presented as crude and adjusted odds ratios (OR) with 95% confidence intervals (CI) as shown in table 5.

Replication analysis

Univariable and multivariable binary logistic regression models will be used, as described above, to replicate findings from the identification analysis within the BACE-D material. The results will be presented as crude and adjusted odds ratios (OR) with 95% confidence intervals (CI) as shown in table 5. The decision on whether findings are replicated will be based on the size and direction of the association, the confidence interval and the p-value for each of the predefined prognostic factors [30].

Sample size

This study contains secondary analyses embedded in the BACE-N and the BACE-D study. Details on sample size calculation are provided in the BACE-N (ClinicalTrials.gov Identifier: NCT04261309) and the BACE-D protocol [1].

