To determine statistical power of this study we used number of events per variable (EPV) [46-50] and the rule-of-thumb of “10 events per 1 analysed variable” [51-54]. With a sample size of 450 participants within the BACE-N study, we anticipate 112 participants to be in the top 25th percentile of costs due to healthcare utilization and categorised as having high costs (yes/no) due to healthcare utilization (events). An EPV of 10 will allow a maximum of 11 prognostic variables to be included in

SAP Modifiable prognostic factors of high cost related to healthcare utilization among older people seeking primary care with a new episode of back pain - an identification and replication study (working title)

the final multivariable prediction model. With a sample size of 675 participants in the BACE-D, we anticipate 168 participants to be in the top 25th percentile of costs due to healthcare utilization and defined as having high costs (yes/no) due to healthcare utilization (events). An EPV of 10 will allow a maximum of 16 prognostic variables to be included in the final multiple prediction model.

[Sensitivity analysis](#)

To assess the robustness of the results complete case analysis (without using imputation for missing data) will be carried out as a sensitivity analysis.

6. Selection bias, information bias and covariates

[Selection bias:](#)

Because of limited resources and practical reasons related to recruitment from a broad network of clinicians, the BACE-N and the BACE-D lacks information on eligible study participants that declined to participate or for other reasons were not invited. In order to assess representativeness, the BACE-N study sample will be compared on key sociodemographic variables with a sample from the longitudinal population study of people in the second half of life; The Norwegian study on life course, ageing and generation (NORLAG). The NORLAG study is expected to represent a representative sample of older people with musculoskeletal complaints.

Response rate at each assessment point and reasons for loss to follow-up will be reported. Key baseline characteristics will be compared between those lost to follow-up and those remaining in the study.

[Information bias:](#)

To reduce the risk of information bias, the study outcome (costs) will be measured in an identical manner in all included cases, and in the best possible way within the framework of the BACE-N and the BACE-D study.

[Covariates:](#)

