Weekly							
Monthly or less							
Frequency of use muscle relaxants, sleep medication, N (%)							
Daily							
Weekly							
Monthly or less							
Examinations							
Patients with additional diagnostic examination, N (%)							
Blood sample							
X-ray							
MRI/CT scan							
Others							
Secondary care							
Patients with back operation, N (%)							
Patients with hospitalization, N (%)							
Duration of stay in days, median (IQR)							
Patients with rehabilitation stay, N (%)							
Duration of stay in days, median (IQR)							

SAP Modifiable prognostic factors of high cost related to healthcare utilization among older people seeking primary care with a new episode of back pain - an identification and replication study (working title)

Table 4 Cost related to healthcare utilization from 0-12 month*

	BACE-N	BACE-D
Primary care		
General practitioner		
Medical specialist		
Occupational physician		
Physiotherapist		
Chiropractor		
Manual therapist		
Naprapath		
Psychologist		
Other therapists		
Back medication		
Paracetamol		
NSAID, cortisone		
Muscle relaxants, sleep medication		
Examinations		
Blood sample		
X-ray		
MRI		
CT		
Others		
Secondary care		
Back operation		
Hospitalization and/or rehabilitation stay		
Total costs		

Values are median (interquartile range) of costs (€). *Cost related to healthcare utilization for the entire follow-up period is calculated on basis of the three (BACE-N) and four (BACE-D) follow-up periods

Table 5 Binary logistic regression analyses; individual associations between modifiable prognostic factors and high costs related to healthcare utilization (dependent variable)

	BACE-N		BACE-D	
	Crude OR (95% CI)	Adjusted OR* (95% CI)	Crude OR (95% CI)	Adjusted OR* (95% CI)
Pain severity (NRS, 0-10)				
Disability (RMDQ, 0-24)				
Health-related QOL (SF36, 0-100)				
Physical component				
Mental component				
Emotional well-being (CES-D 0-60)				
Kinesiophobia (FABQ-PA 0-24)				
Comorbidity (SCQ, 0-15)				
Radiating pain below the knee				
Yes				
No				
Expectation of recovery within 3 months, N (%)				

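### Apart from back operations, the high-cost outcome is built from 9 observed months in BACE-N and 12 in BACE-D, and the replication analysis does not allow for this

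*Combined protocol and SAP*

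**What the plan says.** All references are to the SAP on modifiable prognostic factors of high cost, dated 11.03.2021.

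- **Outcome variable (section 4).** The outcome is "costs related to healthcare utilization aggregated for one year of follow up and dichotomized as high and low". The cut is relative: "Having high costs related to healthcare utilization is defined as patients with costs in the top 25th percentile".
- **Recall.** "All variables, except back operations, will be reported with a 3 month recall period", with reporting "at 3, 6, and 12 months follow-up for the BACE-N, at 3, 6, 9, and 12 months follow-up for the BACE-D". The exception is operations: "Back operations will be reported with a 12 month recall period at 12 months follow-up", with no distinction between cohorts.
- **Preparatory analysis (section 5).** Use is calculated separately for 0-3, 3-6 and 9-12 months in BACE-N, and for those windows plus 6-9 months in BACE-D.
- **Table 4.** The table is headed as 0-12 month cost for both cohorts. Its footnote says the total "is calculated on basis of the three (BACE-N) and four (BACE-D) follow-up periods".
- **Replication analysis.** The same logistic models are used "to replicate findings from the identification analysis within the BACE-D material". The decision rests on the size and direction of the association, its interval and its p-value.
- **Information bias (section 6).** "the study outcome (costs) will be measured in an identical manner in all included cases", followed by a qualification that this is done as well as each study's framework permits.

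The SAP states no scaling or filling of BACE-N months 6-9 and no restriction of BACE-D to the BACE-N windows. The multiple-imputation rule does not mention the gap, which affects every BACE-N patient. The only sensitivity analysis is complete case.

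**The concern.** Replication is the second of the study's two aims. A replication asks whether the same association appears when the same quantity is measured in a new sample. Here the dependent variable has one name in both cohorts but is summed over different patient time. Months 0-6 make up two thirds of the observed time in BACE-N and half in BACE-D, so the Norwegian outcome leans towards early care. If a factor mainly drives early use, or mainly drives persistent use, the expected odds ratio differs between the two constructions even when the underlying associations are the same. That difference is systematic and does not shrink with sample size. The replication rule gives no way to separate it from a real difference between the cohorts.

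Table 4 has a related descriptive problem. It sets two cost columns side by side under one 0-12 month heading, although for most items one of them leaves out a quarter of the year.

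**Working it through.** **1. Reproduce the SAP's event counts (Sample size section).**
- BACE-N: 450 × 0.25 = 112.5, stated as 112; 112/10 gives 11 variables.
- BACE-D: 675 × 0.25 = 168.75, stated as 168; 168/10 gives 16 variables.

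Both reproduce. Because the cut is a quarter within each cohort, changing the windows leaves these counts as they are and changes only who is in the top quarter.

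**2. Observed time, for all items except back operations.**
- BACE-N: 3 windows × 3 months = 9 months; 9/12 = 75% of the year.
- BACE-D: 4 windows × 3 months = 12 months; 12/12 = 100%.
- Share of observed time in months 0-6: 6/9 = 67% in BACE-N, 6/12 = 50% in BACE-D.

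**3. How many patients change class?** The documents give no cost distribution, so this can only be illustrated. Two simulations with different assumptions compared the top quarter on four windows with the top quarter on three (months 6-9 dropped).

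| Assumptions | 12-month top-quarter patients outside the 9-month top quarter |
|---|---|
| Log-normal window costs with 30-50% non-users, between-window correlation 0.3-0.7, use flat to halving | 4-15% |
| Log-normal window costs (log-SD 1.0-1.5), correlation of log costs 0.2-0.8, mean flat or declining | 6-18% (about 9 to 31 of 168 in BACE-D; 3-9% of all patients reclassified) |

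In the first simulation, dropping the window lowered mean cost by 11-24%, which bears on Table 4.

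**4. Does simple scaling remove the mismatch?** No. Multiplying the 9-month sum of the recall items by 4/3 keeps every patient's rank, and it changed no classification in the second simulation. Filling months 6-9 with the mean of the two neighbouring windows left 6-19% of the 12-month top quarter misclassified, no better than leaving the gap.

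**5. Effect on the odds ratio per SD of a factor (first simulation).**
- Stable effect over time: 2.44 on 9 months against 2.60 on 12 months; 2.44/2.60 = 0.94, about 6% lower with the gap.
- Fading effect: 1.64 against 1.56; 1.64/1.56 = 1.05, about 5% higher with the gap.

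**6. Set this against sampling error.** The model-based standard errors below assume a normal factor, 25% events, a crude model and complete data, with n = 450 for the 9-month and n = 675 for the 12-month odds ratio.

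| 9-month OR (95% CI) | 12-month OR (95% CI) | Difference in log OR | SE of difference | Ratio |
|---|---|---|---|---|
| 2.44 (1.88-3.16) | 2.60 (2.09-3.23) | 0.064 | √(0.132² + 0.111²) = 0.172 | 0.37 |
| 1.64 (1.31-2.06) | 1.56 (1.30-1.87) | 0.050 | √(0.116² + 0.094²) = 0.149 | 0.33 |

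In both examples the direction is unchanged and the shift is about a third of the standard error of the between-cohort difference.

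**The case against.** The strongest reply is that little follows from the mismatch. The shifts in step 6 are small against sampling error, so the replication decision would rarely change on this account alone. The sizes also rest on invented cost patterns. The simulations leave out back operations, which both totals share over 12 months and which would probably reduce the reclassification; by how much is unknown, because the prices in Table 1 are blank. This stands, and it is why the point is a cheap improvement and not a serious defect.

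Four stronger readings might be inferred, and the documents do not support them.
- *The whole BACE-N outcome covers 9 months.* It does not; back operations cover 12.
- *The difference is hidden.* It is not. The preparatory analysis, Table 3 and the Table 4 footnote all show three against four periods. What is missing is any use of that fact in the replication analysis.
- *The information-bias sentence is plainly false.* It can be read as uniform measurement within each cohort, limited by what each study collected. It is ambiguous across cohorts and needs rewording.
- *The shortened BACE-D total must become the main replication outcome.* The stated outcome is one-year cost, which BACE-D observes in full for these items. Cutting it moves BACE-D away from that definition to copy a BACE-N limitation. This is a trade-off for the sponsor to settle.

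It is also true that matching the windows does not make the outcomes identical. Hospital days are in BACE-N only and prices are national. Those differences cannot be removed by recutting the windows, whereas this one can.

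**Conclusion.** The point holds in a limited form. For all items except back operations, the identification outcome rests on 75% of the year and the replication outcome on 100%; this comes directly from the SAP. Event counts stay at 112 and 168. Under assumed cost patterns, roughly 4-18% of top-quarter patients change and odds ratios move by up to about 6%, in either direction depending on whether a factor's effect persists or fades. These are ranges under assumptions, not estimates for these cohorts. A reader might conclude that the replication is invalid, or that a failed replication would be an artefact of the windows; neither follows from shifts of this size. What remains is an avoidable difference in a comparison that is the study's second aim, with no planned analysis that would show how much it matters.

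**What to change.** 1. Prespecify a BACE-D replication analysis in which total cost and its 75th percentile are computed from 0-3, 3-6 and 9-12 months plus 12-month back operations. Report it beside the four-window result and use it when judging replication. Which of the two is labelled main is the sponsor's choice, to be fixed before analysis so that it cannot depend on which one replicates.
2. In Table 4, show BACE-D on both bases and head the BACE-N column as 9 observed months (operations 12 months).
3. Reword the information-bias sentence to say that the observation windows differ between the cohorts.
4. State as remaining limits that hospital days enter the BACE-N cost only and that unit prices are national.

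The cost is one extra derivation in BACE-D, one extra set of results and some wording. No new data are needed, and no information is lost because the four-window result is still reported.

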Back pain is common in all age groups (1), and one systematic review highlights that disabling back pain is more prevalent in older people than in younger people (2). The clinical course of back-related disability in older adults with back pain has not been extensively studied. Two studies suggests that improvements in disability were modest the first three months, with little to no improvements on group level after three months (3, 4). It is well documented that number of comorbidities are associated with the clinical course of back-related disability in older adults, but the prognostic value of comorbidity is still highly uncertain (5-11).

Study aim:

The primary aim of this study is to examine the clinical course of back-related disability measured at baseline, 3, 6 and 12 months after a new episode of back pain. The secondary aim is to assess the prognostic value of number and severity of comorbidity at baseline for changes in back-related disability over one year of follow-up.

Study design and method

Study design

BACE-N is based on the previously published BACE study protocol from the BACE international consortium (12). The BACE-N protocol has been published (ClinicalTrials.gov Identifier: NCT04261309).

The BACE-N study is a prospective observational cohort study with a 2-year follow-up time. This study will use data from baseline, 3, 6 and 12 months of follow-up. Design of the study was made within the framework PROGnosis RESearch Strategy (PROGRESS), which is a framework for ensuring and enhancing the quality of prognostic studies (13). The primary aim is relating overall prognosis, and the secondary aim is relating confirmatory prognostic factor research (13, 14).

Study population

Patients aged ≥ 55 years visiting a general practitioner (GP), physiotherapist or chiropractor for a new episode of back pain are invited to participate in the study. Back pain is defined as pain located in the region from the top of the scapula to the sacrum, with or without radiating leg pain. An episode of back pain is defined as “new” if the patient has not received health care for the same back complaint during the last 6 months. The exclusion criteria were: Difficulty completing the study questionnaires due to language or cognitive difficulties, mobility impairments impeding the clinical examination (wheelchair-bound patients), had received healthcare for the same back complaint during the last 6 months (notwithstanding care initiated within the previous 4 weeks from time of baseline assessment).

Data collection

At baseline, patients receive a clinical examination and questionnaire. Patients are then given a follow-up questionnaire either through email or mail at 3-months, 6-months and 12-months follow-up.

Description of treatment received during follow-up

The study participants continue their health care in agreement with their healthcare provider regardless of inclusion in the study. This means that patients may receive education and advice, exercise therapy, massage, manipulations, mobilizations, pharmacological therapy, or additional diagnostic testing and referrals, all of which constitutes “usual” primary care (15). Treatment given is at the discretion of the healthcare provider and the patient.

Variables

Outcome measure:

Back-related disability, measured using the Norwegian, validated version of the Roland-Morris Disability Questionnaire (RMDQ) (16, 17). This is a questionnaire with 24 statements regarding abilities to perform ADL tasks, with a dichotomous yes/no answer. The answers are summed to a total score ranging from 0-24, where 0 indicates no disability and 24 indicates “maximum” disability. RMDQ has been found to measure several dimensions of back-related disability (18). We plan to use RMDQ as a continuous measure, as recommended by the PROGRESS framework (14). This will ensure easier comparability to similar studies, and easier inclusion in future meta-analyses.

RMDQ is measured at baseline, 3 months, 6 months and 12 months.

Prognostic factor measurement:

The prognostic factor of interest is comorbidity measured at baseline with a modified version of the Self-administered Comorbidity Questionnaire (SCQ) (19). The original questionnaire measures 13 pre-specified comorbidities, and 2 non-specified. The item “back pain” has been removed for this study and replaced with an additional non-specified item. Thus, the count of comorbidity ranges from 0-15. The diseases listed are: Heart disease, high blood pressure, lung disease, diabetes, ulcer or stomach disease, kidney disease, liver disease, anemia or other blood disease, cancer, depression, osteoarthritis, rheumatoid arthritis and up to 3 non-specified comorbidities. The SCQ measures comorbidities on three levels: 1) Do you have the problem? 2) Do you receive treatment for it? 3) Does it limit your activities? All levels are answered on a dichotomous yes/no level, and you only answer level 2 and 3 if you have answered “yes” on level 1. An individual can receive a maximum of 3 points for each medical condition: 1 point for the presence of a comorbidity, 1 point if they receive treatment for the condition, and 1 point if the condition limits their functioning. The maximum score for the full SCQ is thus 45 points.

We plan to use SCQ part 1 comorbidity count (0-15 scale), and the full SCQ (0-45) in separate models. Previous studies have found linear relationships between comorbidity and back-related disability (7, 11), and thus we plan to treat these variables as linear. Linearity with outcome will be assessed, and deviations will be handled appropriately.

Covariates:

Covariates are presented in table 1. They are chosen based on being “established” prognostic factors in the literature, having been utilized in similar studies previously (to enhance comparability), and for being readily available and easy to measure in clinical practice.

Table 1: Covariates, measurement level and/or instrument, rationale for inclusion		
Factor	Measurement level	Rationale
Age	Continuous, minimum age ≥ 55	Standard covariate in previous studies (7, 8, 10), and in some studies reported to be associated with disability levels in older adults (4, 6, 20)
Sex	Dichotomous	Standard covariate in previous studies (7, 8, 10), and in some studies reported to be associated with disability levels in older adults (6, 20)
BMI	Measured continuous, divided into categories: <20, 20-25, 25-30, <35	Covariate in previous study (7), and found to be associated with disability in older adults (4, 21)
Back pain duration	Measured in days, but categorized to an ordinal scale of 3 categories: 0-6 weeks, 6-12 weeks, >12 weeks, similar to other BACE studies (22)	Covariate in previous study (8), and found to be associated with disability in older adults (4, 6, 11, 20)
Baseline disability	Continuous. Roland-Morris disability questionnaire, 0-24 scale.	Standard covariate, given the outcome is disability. Only applicable if not using mixed models.
Pain severity last week	Continuous. Numeric rating scale 0-10.	Associated with disability in one study in older adults (4).
Expectation of recovery within the next three months	5-point ordinal Likert scale. From “I am fully recovered” to “I am worse than ever”.	Consistently associated with disability in older adults (4, 6, 11)

Statistical power consideration

The published protocol for the BACE-N study estimates that we need a total of 450 patients included in the study. Allowing a 15% dropout rate at 12 months, we will have approximately 380 participants available at 12 months.

We used the power estimation tool in Stata to determine level of statistical power. With a sample size of 450, and an estimated r^2 of 0.30 for the full model of comorbidity adjusted for covariates, we have over 90% power to detect an r^2 -change of 0.017 or higher when adding comorbidity to the model.

Handling of missing data

Missing data will be handled with multiple imputation, using 5 imputations and 10 iterations unless the missing exceeds 30% and missing at random cannot be assumed. We will use the fully conditioned specification method, and regression estimation. For variables where we are unable to use regression estimation due to computational difficulties, predictive mean matching will be used (23).

Missing values for RMDQ will be handled by replacing missing items with the mean of the answered items for the individual, if less than 30% of the items are missing.

A mixed model, which we intend to use for the primary and secondary aim, does not require variable level imputation for the outcome measure. However, missing values on item level on

the RMDQ might still be an issue. To solve this, we will replace missing items for RMDQ with the mean of the answered items for the individual, if less than 7 (30%) of the 24 items are missing.

Statistical analyses

General statistical considerations

Analyses described in this statistical analysis plan are considered a priori analyses. Possible post-hoc exploratory analyses will be explicitly identified in the article. All analyses will be carried out by the first author using Stata version 16, under supervision from the principal investigator and the advisory statistician. The statistical tests will be 2-sided, and p-value will be reported. If the p-value is less than 0.05, the test is deemed statistically significant. 95% confidence intervals will be reported on point estimates.

Statistical analyses

Description of study flow and study sample:

The flow of participants will be reported with a flow chart. Reasons for exclusion and loss to follow-up will be provided where known. Descriptive data of the study sample will be reported using mean and standard deviation for normally distributed continuous variables, median and interquartile range for variables with skewed distribution, and with frequency and proportions for categorical variables. Normal distribution will be examined visually using histogram and QQ-plot, and statistically with the Kolmogorov-Smirnov test. Baseline characteristics will be presented in a table. See proposed tables and figures below.

Descriptive statistics will be used to present the mean and standard deviation if RMDQ is normally distributed, or median and interquartile range if RMDQ is not normally distributed, for each time point: Baseline, 3 months, 6 months, 12 months. This will also be presented graphically, similarly to van der Gaag et al (3). This graphical presentation will also be performed stratified for number of comorbidities.

A person may be a responder at one time-point and a non-responder at another. Therefore, an analysis of responders versus non-responders will be performed for each time point, using bivariate analysis for baseline characteristics (chi square test, Individual Samples T-test, or Mann Whitney U-test). Results from these analyses will be presented in text, and the table available in supplementary material.

Model choice and model building strategy:

According to the STRATOS initiative task force, a complete prespecifying of all aspects in model building is unrealistic in observational studies (24). Thus, the following will provide a framework for analysis and model building in this study, not a detailed recipe. Decisions regarding final choice of models will be made by the first author, the advisory statistician and the principal investigator.

Primary aim, clinical course of back-related disability:

Mixed models for repeated measures will be used to account for statistical dependencies. RMDQ is the dependent variable, and time and first contact health provider will be entered as fixed factors. The exact handling of time as a continuous or categorical variable depends on the distribution. Previous studies have found that the clinical course of a back episode is not linear over time (3, 25, 26). It is therefore reasonable to believe that time will have to be treated as a categorical variable, or by introducing a quadratic term, depending on its distribution. Choice of covariance matrix is dependent on data structure. Interaction between first contact health provider and time will be analysed.

Secondary aim, prognostic value of number and severity of comorbidities on the course of back-related disability:

We will fit separate models for count of comorbidity (SCQ part 1, 0-15 scale) and count and severity of comorbidity (full SCQ, 0-45). The steps are outlined below:

1. The univariate association between SCQ and RMDQ over time will be assessed with a mixed model for repeated measures. An interaction term for SCQ*time will be tested, and kept if statistically significant. We will present the crude regression estimates from this analysis.
2. A mixed model with all the covariates from Table 1 and RMDQ over time will be fitted. From this model, r^2 will be presented as a measure of prognostic value.
3. SCQ will be added to the model from step 2. The adjusted regression estimate, and the r^2 -change from step 2 to step 3 will be presented.

Previous studies have found a linear relationship between number and severity of comorbidity and disability (7, 27). Linearity between SCQ and RMDQ will be assessed with a scatter-plot. In case of non-linearity between SCQ and RMDQ comorbidity count and disability score, the following alternatives will be discussed (24, 28):

- Categorization of SCQ
- Transformation (logarithmic or cubic) of SCQ
- Fractional polynomials for SCQ
- Spline functions for SCQ

Sensitivity analyses

Complete case analyses will be performed to assess possible bias introduced by the multiple imputation procedures.

Proposed tables and figures

[figure not shown]

Figure: Flowchart of study participants

Baseline characteristics:

Table: Baseline characteristics

Variable	n	Values
Sociodemographic variables		
Age, median (IQR)		
Female, n (%)		
Married or living with partner, n (%)		
Education level high, n (%)		
General health variables		
Health-related quality of life (SF-36), median (range)		
Physical component score		
Mental component score		
Hazardous alcohol consumption (AUDIT-C), n (%)		
Smoking status, n (%)		
Current smoker		
Smoked previously		
Never		
Falls efficacy (FES-I), median (range)		
Back pain history and characteristics of current episode		
First healthcare provider		
General practitioner		
Physical therapist		
Chiropractor		
History of back pain, n (%)		
Using pain medication, n (%)		
Sleep problems weekly due to back pain, n (%)		
Back pain (NRS 0-10) (figure?), median (range)		
Disability (RMDQ 0-24) (figure?), median (range)		
Duration of current episode, n (%)		
0 – 6 weeks		
6 weeks – 3 months		
> 3 months		
Psychological variables		
Kinesiophobia (FABQ-PA 0-28), median (range)		
Depression (CES-D 0-60), median (range)		
Pain catastrophizing (PCS 0-52), median (range)		
Back beliefs and attitudes (BBQ 9-45), median (range)		
Expectations of back pain next 3 months (figure?), n (%)		
Fully recovered		
Much better		
No change or worse		
Psychosocial risk profile (SBT)		
Low risk		
Medium risk		
High risk		
Clinical variables		
Pain with active movements of the back, n (%)		
Positive radiculopathy diagnostic rule, n (%)		
Two or more red flags, n (%)		
Physical performance (BPS), median (range)		
Functional mobility (TUG), median (range)		

SF-36, Short Form health survey 36; AUDIT-C, alcohol use disorders identification test, score ≥ 3 for women and ≥ 4 for men ; FES-I, Falls Efficacy Scale – International; NRS, numeric rating scale; RMDQ, Roland-Morris Disability Questionnaire; FABQ-PA, Fear-Avoidance Beliefs Questionnaire – Physical Activity; CES-D, Center for Epidemiological Studies – Depression; PCS, Pain Catastrophizing Scale; BBQ, Back Beliefs Questionnaire; SBT, Start Back Tool; BPS, Back Performance Scale; TUG, Timed Up-and-Go.

*Comorbidities measured with Self-administered Comorbidity Questionnaire and a question on osteoporosis.

